4.1.4 Drug assignment and administration of doses for each subject

This trial consists of two parts:

Part 1 is an open-label, two-treatment, two-period, one fixed sequence cross-over trial, in which all subjects will first receive BI 425809 (treatment A = Reference 1) alone and then again after multiple doses of donepezil (treatment B = Test 1).

The treatments to be evaluated in Part 1 are outlined in [Table 4.1.4: 1](#) below.

Table 4.1.4: 1 Part 1: Dosage and treatment schedule

Treatment	Substance	Formulation	Unit strength	Dosage	Total dose
A (Reference 1)	BI 425809	Tablet	25 mg	1 tablet (Day 1, Visit 2)	25 mg
B (Test 1)	Donepezil	Tablet	5 mg	1 tablet (Day 1-7, Visit 3) q.d. 2 tablets (Day 8-28, Visit 3) q.d.	245 mg
	BI 425809	Tablet	25 mg	1 tablet (Day 22, Visit 3)	25 mg

Part 2 has an open-label two-treatment, two-period, one fixed-sequence cross-over design. In Part 2 all subjects will first receive donepezil (treatment C = Reference 2) alone and then again after multiple doses of BI 425809 (treatment D = Test 2).

The treatments to be evaluated in Part 2 are outlined in [Table 4.1.4: 2](#) below.

Table 4.1.4: 2 Part 2: Dosage and treatment schedule

Treatment	Substance	Formulation	Unit strength	Dosage	Total dose
C (Reference 2)	Donepezil	Tablet	5 mg	2 tablets (Day 1, Visit 2)	10 mg
D (Test 2)	Donepezil	Tablet	5 mg	2 tablets (Day 10, Visit 3)	10 mg
	BI 425809	Tablet	25 mg	1 tablet (Days 1-24, Visit 3) q.d.	600 mg

Trial medication will be administered to fasted subjects only (for fasting periods please refer to [Section 4.2.2.2](#)). The investigator (or authorised designee) will administer the trial medication as an oral dose together with about 240 mL of water to subjects who are in a standing position. For drug administration, the so-called four-eye principle (two-person rule) should be applied. For this, one authorised employee of the trial site should witness the administration of trial medication, and – if applicable – its preparation (e.g. reconstitution), if correct dosage cannot be ensured otherwise.

In **Part 1**, subjects will be kept under close medical surveillance until 38 h following administration of BI 425809 on Day 1, Visit 2 and on Day 22 Visit 3. In addition subjects will remain under medical supervision for about 14 h following the first dose of donepezil on Day 1 Visit 3. This in-house surveillance period can be extended anytime if deemed necessary based on the medical judgement of the investigator.

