In **Part 2**, subjects will be kept under close medical surveillance until at least 72 h following administration of donepezil on Day 1(Visit 2) and Day 10 (Visit 3).

There will be no wash-out period between treatments A/C and B/D in Part 1 and 2, respectively as the extended blood sampling phase already covers a sufficiently long wash-out between the drug administration of treatment A/C and the first drug administration in treatment B/D. Therefore the first day of treatment B/D, i.e. Visit 3, follows immediately after the last day of treatment A/C, i.e. Visit 2, but these two days are not the same day.

For restrictions with regard to diet see [Section 4.2.2.2](#).

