On treatment BI 425809+ donepezil	Don + BI part 1	Combination of two phases: First phase: Date/time of first administration of donepezil Second phase: Date/time of second administration of BI 425809	Combination of two phases: First phase: Date/time of first administration of BI 425809 + 11*24h (i.e. REP of BI425809 of 11 days) Second phase: Date/time of second administration of BI 425809 + 11*24h (i.e. REP of BI425809 of 11 days)
Follow-up	F/U part 1	Date/time of last administration of donepezil + 15*24h (i.e. REP of donepezil of 15 days)	00:00 a.m. on day after subject's trial termination date

The planned duration of the analysis phase of BI part 1 is 8 days, of Don part 1 it is 28 days and of Don + BI part 1 it is 14 days.

Table 6.1: 4 Analysis phases for statistical analysis of AEs, vital signs, safety laboratory data and visual tests, part 2

Study analysis phase	Label	Start	End
Screening	Screening part 2	Date of informed consent	Date/time of first administration of Donepezil
On treatment donepezil	Don part 2	Date/time of first administration of donepezil	Date/time of first administration of donepezil + 15*24h (i.e. REP of donepezil of 15 days)
On treatment BI 425809	BI part 2	Combination of two phases: First phase: Date/time of first administration of BI 425809 Second phase: Date/time of second administration of donepezil + 15*24h (i.e. REP of donepezil of 15 days)	Combination of two phases: First phase: Date/time of second administration of donepezil Second phase: Date/time of last administration of BI 425809 + 11*24h (i.e. REP of BI 425809 of 11 days) or 00:00 a.m. on day after subject's trial termination date whatever occurs earlier
On treatment BI 425809+ donepezil	BI + Don part 2	Date/time of second administration of donepezil	Date/time of second administration of donepezil + 15*24h (i.e. REP of donepezil of 15 days)
Follow-up	F/U part 2	Combination of two phases: First phase: Date/time of first administration of donepezil + 15*24h (i.e. REP of donepezil of 15 days) Second phase: Date/time of last administration of BI 425809 + 11*24h (i.e. REP of BI 425809 of 11 days)	Combination of two phases: First phase: Date/time of first administration of BI 425809 Second phase: 00:00 a.m. on day after subject's trial termination date

The planned duration of the analysis phase of Don part 2 is 15 days, of BI part 2 it is 19 days and of BI + Don part 2 it is 15 days.

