AE displays in CTR Section 15.3, Appendix 16.1.13.1.8.2 and Appendix 16.1.13.1.8.3 will present results for the on-treatment phase only.

In AE tables in CTR Section 15.3 (but not in Appendix 16.1.13.1.8.2 and Appendix 16.1.13.1.8.3 AE tables), the following total will be provided in addition:

- "**Total on-trt part x**", defined as the total over all on-treatment phases, x will be replaced with 1 or 2 for the respective part
- "**Total BI part x**", defined as the total over all on-treatment phases involving BI, x will be replaced with 1 or 2 for the respective part

CTR Appendix 16.1.13.1.8.1 displays will present results for the screening, on-treatment and follow-up phases.

Additionally to the total defined above, the following total will be provided in AE tables in CTR Section 16.1.13.1.8.1:

- **"Total part x"**, defined as the total over all study phases (screening + on-treatment + follow-up) , x will be replaced with 1 or 2 for the respective part

More details on the technical implementation of these analyses are provided in the ADS Plan of this TSAP.

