7.8.1 Adverse Events

AEs will be coded with the most recent version of MedDRA.

The analyses of AEs will be descriptive in nature. All analyses of AEs will be based on the number of subjects with AEs and not on the number of AEs.

For analysis, multiple AE occurrence data on the eCRF will be collapsed into one event provided that all of the following applies:

- All AE attributes are identical (lower level term, intensity, action taken, therapy required, seriousness, reason for seriousness, relationship, outcome, AESI)
- The occurrences were time-overlapping or time-adjacent (time-adjacency of two occurrences is given if the second occurrence started at most 1 hour after the first occurrence ended)

For further details on summarization of AE data, please refer to "Analysis and Presentation of Adverse Event Data from Clinical Trials" ([7](#)) and "Handling of missing and incomplete AE dates" ([3](#)).

The analysis of AEs will be based on the concept of treatment emergent AEs. That means that all AEs will be assigned to screening, on-treatment or follow-up phases as defined in [Section 6.1](#). AEs will be analysed based on actual treatments, as defined in [Table 6.1: 3](#) and [Table 6.1: 4](#).

An overall summary of AEs will be presented. This overall summary will comprise summary statistics for the class of other significant AEs according to ICH E3 ([8](#)) and for the class of AESIs.

CTP: *The following are considered as AESIs:*

- *Hepatic injury*
A hepatic injury is defined by the following alterations of hepatic laboratory parameters:
 - *An elevation of AST (aspartate transaminase) and/or ALT (alanine transaminase) ≥ 3 -fold ULN combined with an elevation of total bilirubin ≥ 2 -fold ULN measured in the same blood sample, or*
 - *Aminotransferase (ALT, and/or AST) elevations ≥ 10 fold ULN*

The investigator had to classify on the eCRF whether an observed AE was an AESI or not.

According to ICH E3 (8) AEs classified as "other significant" need to be reported and will include those non-serious and non-significant AEs

- (i) which are marked haematological or other lab abnormalities, or
- (ii) which were reported with "action taken = discontinuation" or "action taken = reduced", or
- (iii) which lead to significant concomitant therapy as identified by the Clinical Monitor/Investigator at a Medical Quality Review Meeting.

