The frequency of subjects with AEs will be summarised by treatment, primary SOC and preferred term. AEs which were considered by the investigator to be drug related will be summarised separately. Separate tables will also be provided for subjects with SAEs, subjects with AESIs and subjects with other significant AEs (according to ICH E3 (8)). AEs will also be summarized by maximum intensity.

The SOC and preferred terms within SOC will be sorted by descending frequency over all treatment groups.

For disclosure of AE data on ClinicalTrials.gov, the frequency of subjects with non-serious AEs occurring with an incidence of greater than 5 % (in preferred terms) will be summarised by treatment, primary SOC and preferred term. The frequency of subjects with SAEs will also be summarised.

For disclosure of AE data in the EudraCT register, the frequency of AEs, the frequency of non-serious AEs with an incidence of greater than 5 % (in preferred terms) and the frequency of SAEs will be summarized.

For support of lay summaries, the frequency of subjects with drug-related SAEs will be summarized by treatment, primary SOC and preferred term.

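### SAP Table 6.1: 3: the 14-day Don + BI part 1 phase pools the first 3 days of donepezil with the 11 days after the real co-dose; splitting the row is a cheap improvement, not the correction of an error

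*SAP*

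**What the plan says.** SAP 6.1 divides each subject's time into analysis phases for AEs, vital signs, safety laboratory data and visual tests. In Table 6.1: 3 the start cell of *Don + BI part 1* reads "First phase: Date/time of first administration of donepezil Second phase: Date/time of second administration of BI 425809". The two windows end at the first and the second BI 425809 dose, respectively, plus 11*24h. *Don part 1* begins only at the first BI dose + 11*24h. It stops at the second BI dose and resumes 11 days after it. The planned duration of *BI part 1* is 8 days, and "of Don part 1 it is 28 days and of Don + BI part 1 it is 14 days".

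SAP 7.8.1 says of the AE analysis: "All analyses of AEs will be based on the number of subjects with AEs and not on the number of AEs". It continues: "The frequency of subjects with AEs will be summarised by treatment, primary SOC and preferred term". SAP 6.1 adds a total over all on-treatment phases, a total "defined as the total over all on-treatment phases involving BI", and an appendix total over all study phases. For technical detail it refers to an ADS Plan that is not among the documents.

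The REPs of 11 days (BI 425809) and 15 days (donepezil) come from Protocol 1.2.3. Protocol 7.3.4 assigns events up to the end of the REP to treatment, leaves the exact intervals to the SAP, and permits further intervals there.

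**The concern.** The combination column joins two situations that a safety reader would want to see apart. In the first, subjects take their first three 5 mg donepezil doses and no BI is given; the only BI dose lies 8 to 11 days back. In the second, BI is given on top of donepezil 10 mg.

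The by-treatment AE tables are what a reader uses to attribute events to donepezil alone or to the combination. Protocol 1.2.2 reads the earlier donepezil interaction trial (with another compound) in this way when it reports dizziness under donepezil alone only. The protocol also treats the first donepezil dose as a safety point of its own: "subjects will remain under medical supervision for about 14 h following the first dose of donepezil on Day 1 Visit 3". Events from those hours nevertheless go to the combination column, and none of them can appear in *Don part 1*. At N = 18 one subject is 1/18 = 5.6% of a column, so a few early events could change how it reads.

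**Working it through.** **Inputs, Part 1, in hours from the first BI dose** (Flow Chart; Protocol 1.2.3)

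- Visit 3 Day 1 is the day after Visit 2 Day 8 (168 h), so the first donepezil dose is at 168 + 24 = 192 h.
- Second BI dose, Visit 3 Day 22: 192 + 504 = 696 h.
- Last donepezil dose, Visit 3 Day 28: 192 + 648 = 840 h.
- REPs: BI 11 × 24 = 264 h; donepezil 15 × 24 = 360 h.

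**The SAP's own durations**

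| Phase | Interval (h) | Days |
|---|---|---|
| BI part 1 | 0 to 192 | 8 |
| Don + BI part 1, window 1 | 192 to 264 | 3 |
| Don + BI part 1, window 2 | 696 to 960 | 11 |
| Don part 1, first window | 264 to 696 | 18 |
| Don part 1, second window | 960 to 1200 | 10 |

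The combination phase is 3 + 11 = 14 days and *Don part 1* is 18 + 10 = 28 days, both as stated. The sum 8 + 14 + 28 = 50 days equals the span 1200/24 = 50, so there are no gaps and no overlaps.

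**What the two windows contain**

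- Window 1: donepezil 5 mg at 192, 216 and 240 h (Visit 3 Days 1 to 3), with no BI dose. The Day 4 dose falls on the 264 h boundary. AE questioning after the first donepezil dose is planned at 14, 24, 48 and (pre-dose) 72 h of Visit 3.
- Window 2: one BI dose at 696 h, donepezil 10 mg on Days 22 to 28 (696 to 840 h), then (960 - 840)/24 = 5 days without either drug.

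**Share of the phase**

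Window 1 is 3/14 = 21% of the planned phase, or 18 × 3 = 54 of 18 × 14 = 252 planned subject-days. The other 11/14 = 79% follow an actual co-dose.

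**Part 2 for comparison, in hours from the first donepezil dose**

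The SAP states "of BI part 2 it is 19 days and of BI + Don part 2 it is 15 days". The first BI dose is at 336 + 24 = 360 h, which is exactly 15 × 24, so the donepezil REP leaves no overlap. The second donepezil dose is at 360 + 216 = 576 h and its REP ends at 936 h. That is one 15-day window, all of it after the co-dose.

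**After a split**

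The phases are 8, 28, 3 and 11 days. The on-treatment total is 8 + 28 + 3 + 11 = 50 days and the BI total is 8 + 3 + 11 = 22 days, both unchanged.

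**The case against.** The best defence is that the table does what the protocol asks. The REP is the time in which drug may still be measurable or acting, so donepezil taken within 11 days of BI is, by that rule, donepezil with BI. The windows and the 14 days are stated openly, and Protocol 7.3.4 allows further intervals without requiring them. All of this stands, and it is why the point is an improvement only.

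It also stands that other pooling remains. *Don part 1* mixes 5 mg and 10 mg donepezil with 10 days that begin 5 days after the last dose, and an 11-day combination column would still hold 5 undosed days. The seam at issue differs in that one of the two windows contains no co-dose at all.

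A reader might infer more than the documents support:

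- **That early AEs are lost.** They are not. They stay in both on-treatment totals and in the listings.
- **That only the listings can separate the windows.** This cannot be confirmed without the ADS Plan. What can be said is that no table or total described in the SAP does so.
- **That the combination column is biased in a known direction.** No AE onset times are given, so neither the number of AEs nor the direction can be derived.
- **That the protocol contradicts itself,** because Section 4.1.4 says the sampling phase "already covers a sufficiently long wash-out between the drug administration of treatment A/C and the first drug administration in treatment B/D" while the REP is still running. That statement can be read as serving the PK comparison and the REP as serving safety, so the two can coexist. It is weak support at most.
- **That Part 1 and Part 2 must match.** They use different subjects, swap the roles of the two drugs, and are not compared with each other. The contrast only illustrates the point.

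**Conclusion.** The point holds as an optional improvement to the descriptive safety tables. *Don + BI part 1* is 3 days of donepezil initiation under residual BI plus 11 days from a real co-dose, and AEs of the first 72 h of donepezil are counted as combination AEs without being shown apart in any output the SAP describes. The phase definition is consistent with the REPs and its figures reproduce exactly. No PK result is affected. Vital signs, laboratory values and visual tests are summarised by planned time point, so the effect falls mainly on the AE tables.

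The 21% share is one of planned time, not of events. It assumes dosing at the scheduled times; actual times would shift the boundary slightly.

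**What to change.** In SAP Table 6.1: 3, keeping both REPs:

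- Let *Don + BI part 1* run from the second BI 425809 dose to that dose + 11*24h (planned 11 days).
- Add a separate on-treatment row, for example *Don start + residual BI part 1*, from the first donepezil dose to the first BI dose + 11*24h (planned 3 days).
- Leave *BI part 1* (8 days) and *Don part 1* (28 days) as they are.
- Include both rows in *Total on-trt part 1* (50 days) and *Total BI part 1* (22 days).
- Change the planned-duration sentence to 8, 28, 3 and 11 days.

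The combination column then starts at an actual co-dose and the initiation AEs become visible. The change does not move those AEs into *Don part 1*. Because the tables count subjects, the new column cannot simply be added to *Don part 1* either: one subject may appear in both.

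The cost is a revised SAP and some programming. No new data are needed, and no protocol amendment, since Protocol 7.3.4 provides for such intervals. The downside is one short extra column wherever these phases are used, sparse outside AEs. After the first donepezil dose, vital signs are planned at 14 and 24 h and pre-dose at 72 h, there is one safety laboratory sample at the 72 h boundary, and no visual test is scheduled.

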6.2 IMPORTANT PROTOCOL DEVIATIONS

Consistency check listings (for identification of deviations from time windows) and a list of protocol deviations (e.g. deviations in drug administration, in blood sampling times, etc.) will be provided to be discussed at the Report Planning Meeting (RPM). At this meeting, it will be decided whether a discrepant data value can be used in analyses or whether it must be corrected in the clinical database. Each protocol deviation must be assessed to determine whether it is an important PD (IPD). For definition of IPDs, and for the process of identification of these, refer to the BI reference document "Identify and Manage Important Protocol Deviations (IPD)" (2).

If any IPDs are identified, they are to be summarised into categories and will be captured in the decision log. Categories that are considered to be IPDs in this trial are defined in the integrated quality and risk management plan (IQRMP). If the data show other IPDs, the definition in the IQRMP will be supplemented accordingly by the time of the RPM.

IPDs will be summarized and listed. [Table 6.2: 1](#) below specifies which kind of IPDs could potentially lead to exclusion from which analysis set. The decision on exclusion of subjects from analysis sets will be made at the latest at the RPM, after discussion of exceptional cases and implications for analyses. If the data show other IPDs, this table will be supplemented accordingly by the time of the RPM.

Table 6.2: 1 Handling of IPDs

IPD code	IPD Category & Brief Description	Excluded from which analysis set
A1	Inclusion Criteria Not Met	PKS
A2	Exclusion Criteria Violated	PKS
B1	Informed consent not available/not done	TS, PKS
B2	Informed consent too late	None
C1	Non-compliance	PKS
C2	Incorrect intake of trial medication	PKS
C3	Incorrect trial medication taken	PKS
D1	Prohibited medication use	PKS
D2	Improper washout of prohibited concomitant medication	PKS
E1	Certain violations of procedures used to measure primary or secondary data	PKS
F1	Certain violations of time schedule used to measure primary or secondary data	PKS
G1	PDs affecting safety and rights of subjects	None

6.3 SUBJECT SETS ANALYSED

Subject sets will be used as defined in the CTP, Section 7.3.

Table 6.3: 1 Subject sets analyzed

Class of endpoint	Subject set	
	TS	PKS
Primary PK endpoints		X
Secondary PK endpoints		X
Safety parameters & treatment exposure	X	
Demographic/baseline endpoints	X	

6.5 POOLING OF CENTRES

This section is not applicable, because the study was performed in only one centre.

6.6 HANDLING OF MISSING DATA AND OUTLIERS

Data of screened subjects who were withdrawn from the trial prior to first administration of any study drug will not be reported in the CTR.

Data of subjects who failed to complete all periods of the study (dropouts or withdrawals) will be reported in the CTR as far as their data are available. All withdrawals will be documented and the reason for withdrawal reported in the CTR.

CTP: It is not planned to impute missing values for safety parameters.

One exception where imputation might be necessary for safety evaluation are AE dates. Missing or incomplete AE dates are imputed according to BI standards (3).

Missing data and outliers of PK data are handled according to BI standards (4) and (5).

CTP: PK parameters that cannot be reasonably calculated based on the available drug concentration-time data will not be imputed.

6.7 BASELINE, TIME WINDOWS AND CALCULATED VISITS

Baseline is defined as the last available value before first drug administration.

Time windows are defined in Section 6.1 of the CTP. Adherence to time windows will be checked at the RPM.

7. PLANNED ANALYSIS

The format of the listings and tables will follow the BI guideline "Reporting of clinical trials and project summaries" (6).

The individual values of all subjects will be listed. Listings will be sorted by treatment group subject number and visit (if visit is applicable in the respective listing). AE listings will be sorted by assigned treatment (see [Section 7.8.1](#) below for details). The listings will be contained in Appendix 16.2 (SDL) of the CTR.

The following standard descriptive statistical parameters will be displayed in summary tables of continuous variables:

N	number of non-missing observations
Mean	arithmetic mean
SD	standard deviation
Min	minimum
Median	median
Max	maximum

For plasma concentrations as well as for all PK parameters the following descriptive statistics will additionally be calculated:

CV	arithmetic coefficient of variation
gMean	geometric mean
gCV	geometric coefficient of variation

For PK parameters the following descriptive statistics will additionally be calculated:

P10	10 th percentile
Q1	1 st quartile
Q3	3 rd quartile
P90	90 th percentile

The data format for descriptive statistics of plasma concentrations will be identical with the data format of the respective concentrations. The descriptive statistics of PK parameters will be calculated using the individual values with the number of decimal places as provided by the evaluation program. Then the individual values as well as the descriptive statistics will be reported with three significant digits in the CTR.

Tabulations of frequencies for categorical data will include all possible categories and will display the number of observations in a category as well as the percentage (%) relative to the respective treatment group. Percentages will be rounded to one decimal place. The category missing will be displayed if and only if there actually are missing values. Percentages will be based on all subjects in the respective subject set whether they have non-missing values or not.

